9.3.10 Best Quality Blastocysts 5 Days after Oocyte Retrieval

The best quality blastocyst 5 days after oocyte retrieval at the subject level will be summarized for excellent-quality blastocysts and good-quality blastocysts separately by treatment using descriptive statistics.

9.3.11 Aneuploidy Rate

The aneuploidy rate will be expressed as a percentage for each subject and calculated as 100 times the ratio of the number of aneuploid blastocysts to the total number of blastocysts. Descriptive statistics will be provided by treatment group.

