6.6 Visit 6 - Blastocyst Transfer

On Day 5 following ICSI, a single blastocyst of the best quality available will be transferred; all remaining blastocysts will be frozen using the vitrification method. A transabdominal pelvic ultrasound or transvaginal ultrasound will be performed to assess the endometrial thickness and echogenicity pattern. Laser-assisted trophectoderm biopsy for preimplantation genetic screening (PGS) will be done on Day 5; in the case of late blasulation, biopsy will be performed on Day 6 or Day 7, as needed. All expanded blastocysts with Blastocyst Expansion and Hatching Status 3-6, Inner Cell Mass grading A or B, and Trophoectoderm Grading A, B, or C. (Gardner & Schoolcraft, 1999) should be biopsied. The results of the PGS will not be available prior to the fresh blastocyst transfer, but can be used for subsequent frozen blastocyst transfer cycles, if needed. Adverse events and concomitant medications will be assessed and documented.

Trial Code: 000205

The residual cells obtained from ART (including granulosa cells, immature eggs, eggs that do not fertilize, sperm that is left over after fertilization, or embryos that stop developing, developed abnormally, are aneuploid or that would be discarded after other embryos are selected for embryo transfer or freezing) may be considered for use for further research in a future sub-study. Some of the research may be genetic and/or may be used for some of the following reasons.

- To further our understanding of how patients' genetics affect the response to medications designed for ovarian stimulation.
- To develop new techniques to optimize our understanding of genetic and chromosomal regulation in eggs, sperm, and embryos.
- To improve embryonic efficiency by assessing genes, DNA, RNA, proteins, chromosomes and cellular pathologies.
- To characterize normal and abnormal expression of genes and their functions, as well as downstream effects of transcription and translation.
- To determine the frequency of embryo mosaicism and chromosomal irregularities (inversions, translocations, deletions, etc.)
- To study proteins and their structure, functions, and interactions.

Subjects who wish to participate in such a sub-study will be asked to consent to the donation of this material.

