For blastocysts with expansion and hatching status 3-6, blastocyst inner cell mass grading and trophectoderm grading will be evaluated.

Blastocyst inner cell mass grading will be assessed as 1 of the following:

- A: Tightly packed, many cells.
- B: Loosely grouped, several cells.
- C: Very few cells.
- D: Degenerative or no inner cell mass.

Trophectoderm grading will be assessed as 1 of the following:

- A: Many cells forming a cohesive epithelium.
- B: Few cells forming a loose epithelium.
- C: Very few, large cells.
- D: Degenerative or very large cells.

Date: 10 Dec 2015 E-Protocol Amendment-19588; Ver. 1.0 Supersedes: 28 October 2015 Page 42 of 69

Blastocysts with expansion and hatching status 3-6 will have a score combining the 3 parameters (blastocyst expansion and hatching status, inner cell mass, and trophectoderm); e.g., 4AB for a blastocyst with blastocyst expansion and hatching status 4, inner cell mass grading A, and trophectoderm grading B.

Trial Code: 000205

7.2.9 Overall Blastocyst Quality on Day 5

The overall blastocyst quality on Day 5 is based on the blastocyst expansion and hatching status, inner cell mass grading, and trophectoderm grading.

Excellent-quality blastocysts are defined as those with blastocyst expansion and hatching status 4, 5, or 6, inner cell mass grading A, and trophectoderm grading A or B. The number and percentage of excellent-quality blastocysts on Day 5 is a secondary endpoint. This will be based on the best overall quality score of the Day 5 post-insemination assessments.

Good-quality blastocysts are defined as those with blastocyst expansion and hatching status 3, 4, 5, or 6, inner cell mass grading B, and trophectoderm grading A or B. The number and percentage of good-quality blastocysts on Day 5 will be based on the best overall quality score. The number and percentage of excellent-quality blastocysts and good-quality blastocysts on Day 5 will be calculated. The best blastocyst based on Day 5 morphology will be transferred.

All expanded blastocysts with Blastocyst Expansion and Hatching Status 3-6, Inner Cell Mass grading A or B, and Trophoectoderm Grading A, B, or C. should be biopsied.

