7.2.10 Compaction Assessment in Morulas

Embryos that have not reached the blastocyst stage on Day 5, but are morulas, will also be evaluated. Morulas will be categorized as 1 of the following 3 options:

- Compacted: complete compaction. Tightly compacted cells. Individual cell membranes are no longer visible.
- Compacting: early stage. Cells can be distinguished.

Abnormal compaction: regional or partial compaction, or few cells (<8) in compaction

Day 5 morulas may be considered for extended culture as per the investigator/site standard of care. Day 6 or Day 7 viable blastocysts can then undergo trophectoderm biopsy and vitrification. All expanded blastocysts with Blastocyst Expansion and Hatching Status 3-6, Inner Cell Mass grading A or B, and Trophoectoderm Grading A, B, or C. should be biopsied.

The quality of Day 6 or Day 7 embryos should be assessed and recorded on the eCRF according to the criteria specified in section 7.2.9.

Date: 10 Dec 2015 E-Protocol Amendment-19588; Ver. 1.0 Supersedes: 28 October 2015 Page 43 of 69

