9.6 Efficacy Endpoint Assessments

9.6.1 General Considerations

All primary, secondary, and post-trial efficacy analyses will be conducted for the mITT analysis set. Analyses for the mITT, PP, and ITT analysis sets will be conducted according to the randomized treatment. Analyses for the safety analysis set will be conducted according to the actual treatment received. Continuous variables will be described with the number of non-missing values, mean, standard deviation, median, and minimum/maximum values. Categorical variables will be described with the number and percentage of subjects with each level. Missing values will not be included in the calculation of percentages unless otherwise specified. All individual subject data will be listed.

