- The quality of blastocysts 5 days after oocyte retrieval will be assessed by blastocyst expansion and hatching status, blastocyst inner cell mass grading, and trophectoderm grading. Frequency distributions will be provided for each treatment group at the blastocyst level.
- The best quality blastocyst 5 days after oocyte retrieval at the subject level will be summarized for excellent-quality blastocysts and good-quality blastocysts separately by treatment using descriptive statistics.
- The aneuploidy rate will be expressed as a percentage for each subject and calculated as 100 times the ratio of the number of aneuploid blastocysts to the total number of blastocysts. Descriptive statistics will be provided by treatment group.

Date: 10 Dec 2015 E-Protocol Amendment-19588; Ver. 1.0 Supersedes: 28 October 2015 Page 54 of 69

• Endometrial thickness and the echogenicity pattern will be summarized by frequency distribution and by descriptive statistics, as appropriate, for each treatment group at stimulation Day 6, the last day of stimulation, and at the time of blastocyst transfer in the fresh cycle.

Trial Code: 000205

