9.1.1 Tabulations

All summaries will be presented by treatment group and overall. Categorical data will be summarized using numbers and percentages. The percentages are based on the total number of subjects with a corresponding assessment. Continuous data will be presented using the number of subjects with an observation, mean and standard deviation, median, interquartile range, minimum, and maximum.

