9.1.3 Handling of Drop-Outs and Missing Values

For the primary and secondary endpoints positive β -hCG and clinical pregnancy missing observations will be imputed to negative unless a positive result is observed at a later pregnancy assessment. For example, if the outcome of β -hCG is missing but clinical pregnancy is 'positive' then β -hCG will be imputed as 'positive'.

Missing values will not be imputed for the any of the other secondary endpoints.

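### The aneuploidy rate divides by all blastocysts although only biopsy-grade ones are directed to testing, so untested blastocysts count as not aneuploid

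*SAP*

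**What the plan says.** SAP 9.3.11 expresses the aneuploidy rate per subject as "100 times the ratio of the number of aneuploid blastocysts to the total number of blastocysts" and summarises it descriptively by arm. Protocol 9.6.3 has the same denominator: "the ratio of the number of aneuploid blastocysts to the total number of blastocysts". Neither text limits it to blastocysts that were biopsied or that gave a result.

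Protocol 6.6 says which blastocysts should be biopsied: "All expanded blastocysts with Blastocyst Expansion and Hatching Status 3-6, Inner Cell Mass grading A or B, and Trophoectoderm Grading A, B, or C". Protocol 7.2.9 and 7.2.10 repeat the rule. Late developers are not lost automatically, because under protocol 7.2.10 "Day 6 or Day 7 viable blastocysts can then undergo trophectoderm biopsy and vitrification".

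The grading scale in protocol 7.2.8 is wider than the biopsy rule. It gives blastocyst status to expansion stages 1 and 2, and it grades inner cell mass down to C and D ("D: Degenerative or no inner cell mass") and trophectoderm down to D.

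Three general rules might bear on the point:

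- Protocol 9.6.1: "Missing values will not be included in the calculation of percentages unless otherwise specified".
- SAP 9.1.1: "The percentages are based on the total number of subjects with a corresponding assessment".
- SAP 9.1.3, after dealing with the pregnancy endpoints: "Missing values will not be imputed for the any of the other secondary endpoints".

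**The concern.** The numerator and denominator cover different sets of embryos. A blastocyst can be counted as aneuploid only if it was biopsied and gave a result, but every blastocyst is counted below the line. Unknown ploidy is therefore scored as not aneuploid.

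Two consequences follow. First, the rate is too low in both arms whenever some blastocysts are untested and any are aneuploid. Second, the rate moves with the share tested. That share depends on blastocyst grade, and blastocyst quality is itself a secondary endpoint summarised by arm. A difference in quality between the gonadotropins could thus appear as a difference in aneuploidy. Protocol 1.1 reports that oocyte yield differed between such products in earlier trials. This does not show that tested shares will differ here, but it is a reason not to assume that they are equal.

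**Working it through.** The plan states no expected aneuploidy rate and no expected share tested, so it has no figure of its own to reproduce. The check is of the formula; every rate and share below is an assumption.

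**1. Which blastocysts can enter each part of the ratio**

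| Blastocyst | Denominator as written | Can enter numerator |
|---|---|---|
| Meets the biopsy grade on Day 5, 6 or 7, result obtained | yes | yes |
| Meets the grade, no conclusive result | yes | no |
| Inner cell mass C/D or trophectoderm D | yes | not directed to biopsy |
| Expansion 1–2 that never progresses | yes | not directed to biopsy |

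The documents do not mention inconclusive results. The second row is what the formula implies if any occur.

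**2. Direction of the error**

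For one subject let T be the number tested, U the number untested, A the aneuploid number among those tested, and X the unknown aneuploid number among the untested (0 ≤ X ≤ U).

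- As written: A / (T + U).
- Among tested: A / T.
- Among all blastocysts: (A + X) / (T + U).

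Taking test results as correct, the written rate can never exceed the rate among all blastocysts. It is below the rate among tested whenever U > 0 and A > 0.

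Examples:

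- 5 blastocysts, 3 tested, 1 aneuploid: 1/5 = 20.0% as written, against 1/3 = 33.3% among tested.
- 2 blastocysts, none tested: 0/2 = 0% as written, although nothing is known about ploidy.

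**3. Size in aggregate**

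With a the rate among tested and s the share tested, the written rate is a × s. This is exact when pooled over blastocysts or when s is the same for all subjects. It is approximate if rate and share are correlated across subjects. At s = 0.80:

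- 20% × 0.80 = 16%
- 35% × 0.80 = 28%
- 50% × 0.80 = 40%

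**4. False difference between arms**

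With the same a in both arms, the false difference is a × (gap in s):

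| Gap in share tested | a = 20% | a = 50% |
|---|---|---|
| 0 points | 0 | 0 |
| 5 points | 1.0 | 2.5 |
| 10 points | 2.0 | 5.0 |
| 20 points | 4.0 | 10.0 |

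Equal shares produce no false difference but still understate both arms.

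**5. Check on the mean of per-subject rates**

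A simulation of 400,000 subjects assumed a Poisson number of blastocysts with mean 5, at least 1 per subject, a = 35%, and rate and share independent.

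- s = 0.8: mean 28.0% as written, 35.0% among tested, 1.2% of subjects with none tested.
- s = 0.6: mean 21.0% as written, 35.0% among tested, 4.3% with none tested.

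The none-tested shares agree with the closed form (e^(−5s) − e^(−5)) / (1 − e^(−5)):

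- s = 0.8: (0.0183 − 0.0067) / 0.9933 = 1.2%.
- s = 0.6: (0.0498 − 0.0067) / 0.9933 = 4.3%.

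**The case against.** The strongest reply is that the general rules already exclude untested blastocysts. An unbiopsied blastocyst has a missing ploidy value, protocol 9.6.1 leaves missing values out of percentages, and SAP 9.1.3 forbids imputation. Scoring a none-tested subject as 0% looks like imputing a negative result.

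This has some force. An analyst could use SAP 9.1.3 to set a none-tested subject to missing. But the rules do not settle the matter. Protocol 9.6.1 gives way where something else is specified, and the endpoint specifies the total. SAP 9.1.1 concerns numbers of subjects, not blastocysts within a subject. SAP 9.1.3 does not remove untested blastocysts from the denominator of a partly tested subject. Elsewhere the plan names a restricted denominator when it wants one: SAP 9.3.3 limits early pregnancy loss to subjects with two positive tests.

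The fertilization rate over all retrieved oocytes is not a precedent. Pronuclei are counted on Day 1, so failure to fertilize is observed; the ploidy of an unbiopsied blastocyst is not.

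Other points on that side stand:

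- The biopsy rule is broad and extends to Days 6 and 7, so the untested share may be small.
- SAP 9.2.1 breaks down fresh transfers by genetic result, so the transferred blastocyst does not appear to be systematically untested.
- SAP 9.3.9 will show grade distributions by arm, though not the counts tested.
- The table shells are a separate document and may state the denominator.
- The sponsor may have meant tested blastocysts all along.

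These points limit the likely size and support a modest rating. They do not make the written formula right.

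**Conclusion.** The concern holds on the literal reading of both documents. Followed as written, the formula treats unknown ploidy as not aneuploid, understates the rate, and lets a difference in the share tested look like a difference in aneuploidy.

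The size cannot be established from the documents. The illustrative figures rest on assumed rates of 20% to 50% and assumed tested shares. The 0% score applies to a subject with at least one blastocyst and none tested; with no blastocysts the ratio is 0/0, on which the SAP is also silent.

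The endpoint is descriptive. The primary non-inferiority analysis and the sample size are unaffected. The definition should be corrected because it governs a named secondary endpoint and the correction is cheap. Confidence is medium, mainly because the sponsor's intent may differ from the wording.

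**What to change.** In SAP 9.3.11:

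- Define the denominator as the subject's blastocysts with a conclusive genetic screening result from a Day 5, 6 or 7 biopsy.
- Treat a subject with no such blastocyst as missing for this summary.
- State that the rate describes biopsied, biopsy-grade blastocysts only.
- Report by arm the number of blastocysts, the number biopsied, the number with a conclusive result, and the number of subjects with none.

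Align protocol 9.6.3. If it is not amended, record the change in SAP section 12; protocol section 9 allows departures from its analyses to be described in the SAP or final report.

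The cost is one or two sentences in each document and a changed denominator in the program, since the screening results are already collected. The downside is that subjects with no tested blastocyst leave this summary, and the rate still covers only embryos good enough to biopsy. The added counts make that selection visible but do not remove it.

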9.3.12 Endometrial Thickness and Echogenicity Pattern

Endometrial thickness will be summarized by descriptive statistics and the echogenicity pattern will be summarized by frequency distribution , at stimulation Day 6, the last day of stimulation, and at the time of blastocyst transfer.

9.4 Post-Trial Endpoints

All post-trial endpoints will be summarized using tables and figures, as appropriate. Additional details will be specified in the separate Statistical Analysis Plan for the post-trial endpoints. The post-trial endpoints include:

- Cumulative live birth rate for fresh and frozen blastocyst transfer (defined as the proportion of subjects with at least 1 viable live birth greater >21 weeks gestation).
- Live birth rate for fresh blastocyst transfer (defined as the proportion of subjects with at least 1 viable live birth greater >21 weeks gestation).
- Early pregnancy loss rate in frozen blastocyst transfer is defined as 2 positive β -hCG tests but no ongoing pregnancy at 10-11 weeks gestation in the frozen cycle.
- Late pregnancy loss rate (defined as a confirmed ongoing pregnancy but no viable live birth greater >21 weeks gestation).
- Positive β -hCG rate, clinical pregnancy rate, and ongoing pregnancy rate for frozen blastocyst transfers.

Descriptive statistics will be provided for each of the respective post-trial endpoints.

10 Safety

10.1 General Considerations

Safety parameters will be evaluated for the safety analysis set and subjects will be included in tabulations according to actual treatment received.

10.2 Adverse Events

Adverse events will be recorded from signed informed consent until the end-of-trial visit.

Adverse events (AEs) are classified according to the Medical Dictionary for Regulatory Activities (MedDRA) version 19.1 or later.

Missing values will be treated as missing, except for causality, intensity, seriousness, and outcome of AE. A ‘worst case’ approach will be used:

- if causality is missing, the AE will be regarded as related to the IMP
- if the intensity of an AE is missing, the AE will be regarded as severe
- if seriousness is missing, the AE will be regarded as serious
- if outcome is missing and no date of outcome is present, the outcome is regarded as ‘Not yet recovered’

Missing event start and event stop dates will be imputed in the most conservative way, i.e. the event should start as early as possible based on the (partially) missing start date while remaining treatment emergent (if relevant), and last as long as possible, i.e. until last visit or one day prior to the next event with the same preferred term, if any. In the latter case both consecutive AEs (with the same PT) will remain to be regarded as two separate events (despite being adjacent).

A treatment emergent adverse event is any adverse event occurring in the period from first administration of IMP till end-of-trial visit.

Pre-treatment adverse events will be reported in a listing only. This listing will be sorted by center and subject ID and date of onset.

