- 4. Hemoconcentration is defined as hematocrit >45 %. Electrolyte disturbances are defined as hyponatremia (sodium <135 mEq/L) and/or hyperkalemia (potassium >5.0 mEq/L). Coagulation abnormalities are defined as presence of thromboembolic events, abnormal prothrombin time, or abnormal activated partial thrombin time. Diminished renal perfusion is defined as creatinine >1.2 mg/dL. Oliguria is defined as urine output less than 500 mL/24 hours. Anuria is defined as failure to produce urine. If applicable, actual volume of urine output will be recorded.

All cases of OHSS will be considered AEs and will be recorded in the source documents for that subject and on the AE page in the eCRF. Severe OHSS that requires medical or surgical intervention (i.e., paracentesis or hospitalization) is considered an SAE (see Section 8.4).

Early OHSS is defined as OHSS with onset ≤ 9 days after triggering of final follicular maturation. Classification of grade is according to Golan's classification system (Golan, 1989) and all OHSS cases will be graded as mild, moderate, or severe. Preventive interventions for early OHSS cover cycle cancellation due to excessive ovarian response, triggering of final follicular maturation with GnRH agonist, and administration of dopamine agonist (the latter is only considered as preventive intervention in subjects with ≥ 20 follicles of ≥ 12 mm).

Late OHSS is defined as OHSS with onset >9 days after triggering of final follicular maturation.

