8.2.2 Recording of Adverse Events

The Investigator must record all AEs in the AE Log provided in each subject's eCRF with information about:

- AE description.
- Date and time of onset (time can be omitted, if not applicable).
- Intensity.
- Causal relationship to IMP.

Trial Code: 000205

Date: 10 Dec 2015

E-Protocol Amendment-19588; Ver. 1.0

Supersedes: 28 October 2015

Page 44 of 69

- Action taken to IMP.
- Other action taken.
- Date and time of outcome (time can be omitted, if not applicable).
- Outcome.
- Seriousness.

Each of the items in the AE Log is described in detail in the following sections.

Adverse Event

Adverse events should be recorded as diagnoses, if available. If not, separate signs and symptoms should be recorded. One diagnosis/symptom should be entered per record.

If a subject suffers from the same AE more than once and the subject recovers in between the events, the AEs should be recorded separately. If an AE changes in intensity, a worst-case approach should be used when recording the event, i.e., the highest intensity and the longest duration of the event.^a

Note the following: a procedure is not an AE; the reason for conducting the procedure is. Hospitalization is not an AE; the reason for hospitalization is. Death is not an AE, but the cause of death is (an exception is sudden death of unknown cause, which is an AE).

Date and Time of Onset

The date of onset is the date when the first sign(s) or symptom(s) were first noted. If the AE is an abnormal clinically significant laboratory test or outcome of an examination, the onset date is the date the sample was taken or the examination was performed.

Intensity

The intensity of an AE must be classified using the following 3-point scale:

Mild: Awareness of signs or symptoms, but no disruption of usual activity.

Moderate: Event sufficient to affect usual activity (disturbing).

Severe: Inability to work or perform usual activities (unacceptable).

Exception: if an AE with onset before the first IMP administration (i.e., a pre-treatment AE) changes in intensity, this must be recorded as 2 separate events. The initial AE should be recorded with outcome "not yet recovered" and the date and time of outcome is when the intensity changed. The second AE should be recorded with date and time of onset when the intensity changed.

Trial Code: 000205

Date: 10 Dec 2015 E-Protocol Amendment-19588; Ver. 1.0 Supersedes: 28 October 2015 Page 45 of 69

Causal Relationship to IMP

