10.5 Other Safety Variables

10.5.1 OHSS

A summary table will be prepared showing the incidence and severity of early OHSS, late OHSS, and overall OHSS. This table will display the number and percentage of subjects (%) and the number of events. Early OHSS is defined as OHSS with onset ≤ 9 days after triggering of final follicular maturation. Note this includes OHSS with onset before triggering and OHSS with onset during stimulation where triggering is not performed.

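### The SAP's earliest-possible rule for incomplete AE start dates biases the OHSS early/late split toward early: always when the onset date is wholly missing, and when only the day is missing unless the onset month began more than 9 days after the trigger

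*SAP*

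**What the plan says.** Both documents name the frequency of OHSS, split into early and late at 9 days, as a safety endpoint (Protocol 2.2, SAP 2.2). Protocol 7.1.6 makes every case an AE: "All cases of OHSS will be considered AEs and will be recorded in the source documents for that subject and on the AE page".

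For a missing or partial AE start date, SAP 10.2 imputes conservatively, which it spells out as "the event should start as early as possible based on the (partially) missing start date while remaining treatment emergent". The floor is the first IMP dose, because "A treatment emergent adverse event is any adverse event occurring in the period from first administration of IMP till end-of-trial visit".

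SAP 10.5.1 sets the cut: "Early OHSS is defined as OHSS with onset ≤ 9 days after triggering of final follicular maturation". It then adds: "Note this includes OHSS with onset before triggering and OHSS with onset during stimulation where triggering is not performed". Protocol 7.1.6 gives the other side: "Late OHSS is defined as OHSS with onset >9 days after triggering of final follicular maturation". The output is described as follows: "A summary table will be prepared showing the incidence and severity of early OHSS, late OHSS, and overall OHSS". SAP 10.5.2 also lists early-onset OHSS as a row in the table of signs of excessive response. Neither SAP 10.5.1 nor SAP 10.5.2 has its own rule for incomplete onset dates.

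The protocol has no date imputation. Protocol 9.8.1 leaves missing safety values missing except for four AE attributes, and onset date is not one of them.

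**The concern.** Choosing the earliest possible date makes sense when the question is whether an event is treatment-emergent or how long it lasted. The early/late split asks a different question. Each case goes into one of two rows, so moving doubtful cases in a fixed direction adds to one row what it takes from the other. Here the imputed date can only be pulled back toward the first IMP dose, and early OHSS has no lower bound, so a pulled-back case is never flagged as implausible.

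The split of a named safety endpoint is at stake, together with the early-onset row of the excessive-response table, where a late case with an incomplete date would be counted as a sign of excessive response. The rule can also override what the trial's own visits show about when the event began.

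**Working it through.** The plan gives no figure on this point, so there is none to reproduce. The check applies the written rule to dates.

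**Inputs from the documents.** Imputed onset = the later of (a) the earliest date compatible with the known part and (b) the first IMP date (SAP 10.2). A case is early if imputed onset minus trigger is at most 9 days, with no lower bound (SAP 10.5.1).

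**Assumptions.** The trigger is equally likely on any of the 366 days of 2016. True late onset is d days after trigger, with d from 10 to 45. The first IMP dose is 6, 10 or 20 days before trigger.

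**Date wholly missing.** Imputed onset is the first IMP date, which precedes the trigger. Early in 100% of cases, whatever d is.

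**Only the day missing.** Imputed onset is the 1st of the onset month, or first IMP if later. If the true onset falls on day m of the month, the 1st is d − (m − 1) days after trigger. The case stays late only if d − (m − 1) > 9, that is, m ≤ d − 9. For d up to 38, every month of 2016 contains all the days 1 to d − 9, so

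share turned early = 1 − 12 × (d − 9) / 366.

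| True onset, days after trigger | Calculation | Late cases tabulated as early |
|---|---|---|
| 10 | 1 − 12/366 | 97% |
| 14 | 1 − 60/366 | 84% |
| 21 | 1 − 144/366 | 61% |
| 28 | 1 − 228/366 | 38% |
| 38 | 1 − 348/366 | 5% |
| 40 or more | m ≤ 31 always holds | 0% |

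A direct count over all 366 trigger dates gives the same shares. The stimulation length makes no difference, because the first IMP date always lies before the trigger.

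Any average depends on the onset window assumed. With onsets spread evenly, it is 85% over days 10–17, 79% over days 10–21 and 67% over days 10–28.

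**Day and month missing.** The share turned early is 1 − (d − 9)/366: 99.7% at day 10 and 90% at day 45.

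**Two examples, day missing, true onset 14 days after trigger.**
- Trigger 25 March, onset 8 April: imputed to 1 April, day 7, early. Wrong.
- Trigger 20 March, onset 3 April: imputed to 1 April, day 12, late. Right.

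**Reverse direction.** Imputation never moves an onset later than its true date, so no early case becomes late. The count found none.

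**Against the visit schedule (Protocol Table 1).** Retrieval is about 1.5 days after trigger and transfer (Visit 6) 5 days later, so about day 6.5. Visit 7 is 10–14 days after transfer, about day 16.5 to 20.5. A case absent at Visit 7, first recorded at Visit 8 and lacking an onset date must be late on those records. SAP 10.2 dates it to the first IMP day and it is tabulated as early.

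**The case against.** The strongest reply is that the precondition may never arise. Protocol 8.2.2 asks for "Date and time of onset (time can be omitted, if not applicable"), so only the time may be left out. Suspected OHSS also calls for ultrasound, chemistry and hematology (Protocol 7.1.6), which leave dated records. The documents give no count of incomplete onset dates. This stands, and it limits the point to low priority. It does not remove it, since the SAP itself provides for missing and partial start dates.

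A second reply is that the rule fits the SAP's worst-case approach: putting doubtful cases into the excessive-response table is unfavourable to the drug. That is coherent for that one row. The same step lowers the late row, so it cannot be conservative for the split as a whole, and a shift applied in both arms of a comparison has no built-in worst-case direction.

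A third reply is that the consequence is small. The tables are descriptive, with no planned test, and the rule does not differ by arm. Both statements are correct.

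A reader might infer that every late case with an incomplete date is reported as early. The rule does not do that: with only the day missing, 16% of day-14 onsets and 39% of day-21 onsets stay late, as do all from day 40. A reader might also infer that total OHSS is distorted or that one product is favoured. Overall incidence and severity do not use the onset date, and nothing in the documents suggests that incomplete dates would differ between arms.

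**Conclusion.** The point holds as a one-way bias in the early/late split. A wholly missing onset date is always tabulated as early. A date lacking only the day is tabulated as early unless the onset month began more than 9 days after the trigger. The misclassified share of true late cases then falls from 97% at day 10 to 0% from day 40. These shares rest on trigger dates spread evenly over the year. They are conditional on an incomplete date, and the number of such dates is unknown and may be zero. The point is minor and inexpensive to correct.

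A related inconsistency affects the same tables. Protocol 2.2, SAP 2.2 and SAP 10.5.2 count the 9 days from hCG administration, while Protocol 7.1.6 and SAP 10.5.1 count from triggering. The two differ for subjects given the GnRH agonist trigger, who receive hCG only if a rescue dose is needed (Protocol 6.4).

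**What to change.** In SAP 10.2, 10.5.1 and 10.5.2, state that the imputed start date is not used to assign OHSS to early or late. Instead, form the interval of possible onset dates from everything known: the recorded month or year, the visit at which OHSS was first recorded, the last visit without it, and any dated OHSS work-up. Classify the case as early or late only if the whole interval lies on one side of the 9-day cut. Otherwise show it in a timing-unknown row and count it in overall OHSS. The SAP 10.2 rule can stay for all other AE summaries.

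The known month must be part of the interval. With a trigger on 20 March and onset recorded only as April, onset cannot be before day 12, so the case is certainly late. Visit bounds alone could lose that.

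Reconcile the sections that count from hCG administration with those that count from triggering, so that one anchor applies to every subject.

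The cost is about two sentences and one table row, plus the anchor correction. The downside is that some cases will be shown as timing unknown, notably those bounded only by Visits 6 and 7 (about day 6.5 to day 16.5–20.5), because that interval always spans day 9. Subjects without a fresh transfer do not have those visit bounds and will depend on the other records.
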